3.2.3. Quality of life and symptoms of patients treated conservatively

We will assess Quality of Life and Symptoms of patient who chose conservative management at enrolment and at 3, 12, 24 and 36 months following the diagnosis of SPC. These data will also serve to compare baseline Quality of Life and Symptoms between patients managed surgically and conservatively. We will explore the differences of outcomes of patients who

choose conservative and surgical treatments with adjusting confounding factors. This cohort will also give us an idea about changes in severity of symptoms and QoL over time.

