4.1. INCLUSION CRITERIA

- Age =/> 16 years
- Pineal cyst > 9mm in maximum diameter (Májovský et al., 2017)
- Symptom category B (total score ≥5) according to Eide and Ringstad(Eide and Ringstad, 2017) Figure 1_Eide symptoms
- Willingness and ability to comply with study specific procedures and completion of QoL and symptoms questionnaires.
- Written informed consent

Acta	Neurochir	2017	159:349	-361

Symptom	Severity	Score
Headache	No	0
	Minor-moderate	1
	Severe	2
Nausea/vomiting	No	0
	Yes	1
Dizziness	No	0
	Yes	1
Visual disturbances	No	0
	Yes	1
Episodic loss of consciousness	No	0
	Yes	1
Lethargy/fatigue	None-moderate	0
	Severe	1
Cognitive impairment	No	0
	Minor-moderate	1
	Severe	2
Transient neurological deficits	No	0
	Yes	1
Total score		0/10 - 10/10

Symptom category A (none-moderate), 0–4/10 scores; symptom category B (much-severe), 5–10/10 scores

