4.4.2. Secondary outcomes

The secondary outcomes are:

- 1. Change in all in items of QoL as defined by the EORTC QLQ-C30 questionnaire before and at 3, 12, 24 and 36 months following resection of SPC
- 2. Change of individual symptoms before and at 3, 12, 24 and 36 months following resection of SPC
- 3. Change in the results neuropsychological tests at 12 months following surgery when compared to baseline (before surgery)
- 4. Difference in severity of symptoms and QoL at baseline between patients who chose surgical and non-surgical treatment
- 5. Assessment of symptoms and QoL over (at diagnosis and 3, 12, 24 and 36 months later) in patients who chose not to undergo surgery
- 6. Development of a model to identify anatomical (based in MRI scans) and clinical (symptoms) predictors of improvement of QoL after surgery for SPC

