4.5.2. Symptoms and QoL questionnaires (see Appendices 1-4)

a. Patients who chose surgical treatment

Study participants will undergo surgery as per normal clinical pathway. The participants will be asked to fill in symptom and quality of life (QoL) questionnaires at the entry to the study

(at diagnosis) and at 3, 12, 26 and 36 months after surgery. The participants will be given the options of filling the questionnaire on the paper or on-line.

b. Patients who chose conservative management

The participants will be asked to fill in symptom and quality of life (QoL) questionnaires at the entry to the study (at diagnosis) and at 3, 12, 26 and 36 months after the diagnosis. The participants will be given the options of filling the questionnaire on the paper or on-line.

Once enrolled patients will participate in the study for 3 years, although each participant will be able to leave the study at any time without giving a reason. This will in no way affect their clinical management. This includes the option for patients to choose to undergo surgery at any time even if they have initially elected to pursue conservative management.

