There is no specific time of day when the headache tends to be worse than at other times

When is your 'main headache' least bad?

In the morning

In the evening

Any other time

There is no specific time of day when the headache tends to be better than at other times

Vision

Please tick all boxes next to the statements that apply to you

Blurred vision

Double vision

When turning my head I experience 'delay in seeing the object in front of me'

Tired eyes all the time

What makes your vision-related symptoms worse?

Light

Daylight

Fluorescing light

Computer light

Describe

Eye movement

Looking to the left

Looking to the right

Looking up

In any direction (is there any direction that makes things worse)

Time of day. My vision related problems are worse

Towards the end of the day

In the morning

At night

Do you have any problems when looking up? yes no

If yes – what happens/what symptoms you may get?

Balance problems - dizziness

Which of these statements best describes your symptoms?

I have a sensation of movement - as if I was on a rotating chair/the room is spinning

My legs feel week

I feel like have no control of my legs

I feel light-headed

Time profile

It is there all the time

It starts suddenly

It comes and goes. It lasts for

seconds minutes hours days

It is triggered by movement – describe what sort of movement(s)

Getting up

Suddenly moving my head sideways

Bending my head backwards

Stress

Loud noise

Closing eyes

Is anything that makes your balance worse?

Getting up

Suddenly moving my head sideways

Turning my head backwards

Stress

Loud noise

Closing eyes

Hearing

Reduced hearing problems on the

left right both sides

Hearing noises Hearing voices

Memory

Any memory problems? yes no

Please describe

Speaking

Any speech problems? yes no

Please describe

Concentration

Any problems yes no

Please describe

Sleep problems

I sleep too much

I sleep too little

Other sleep problems. Please describe

Other important symptoms

Please list and describe

Have you been seen by an ENT surgeon?	yes	no
What was their diagnosis/explanation?		
What treatment did they recommend?		
Have you been seen by an ophthalmologist?	yes	no
What was their diagnosis/explanation?		
What treatment did they recommend?		
Have you been seen by a neurologist?	yes	no
What was their diagnosis/explanation?		
What treatment did they recommend?		

6. Study-specific questionnaire – 3-month postoperative

Name sticker	į

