Pineal Cyst Questionnaire – AFTER OPERATION at 3 months

The information that you provide will remain strictly confidential.

As compared to before the operation, overall, I am:

better worse no different

much better much worse

Are you currently at work/school? yes no

Your weight kg

Medications you currently take

	Name	Started	Stopped
HRT			
Contraceptive pill			
Hormonal supplements			
Vitamins			
Painkillers			

Headache

Please tick the box that best describes this symptom after the operation when compared to how it was before the operation.

better worse no different

much better much worse

I no longer have this symptom

I have never had this symptom

Vision

Please tick the box that best describes this symptom after the operation when compared to how it was before the operation.

better worse no different

much better much worse

I no longer have this symptom

I have never had this symptom

Hearing

Please tick the box that best describes this symptom after the operation when compared to how it was before the operation.

better worse no different

much better much worse

I no longer have this symptom

I have never had this symptom

Dizziness/balance problems

Please tick the box that best describes this symptom after the operation when compared to how it was before the operation.

better worse no different

much better much worse

I no longer have this symptom

I have never had this symptom

Memory

Please tick the box that best describes this symptom after the operation when compared to how it was before the operation.

better worse no different

I no longer have this symptom

I have never had this symptom

Speaking

Please tick the box that best describes this symptom after the operation when compared to how it was before the operation.

better worse no different

much better much worse

I no longer have this symptom

I have never had this symptom

Concentration

Please tick the box that best describes this symptom after the operation when compared to how it was before the operation.

better worse no different

much better much worse

I no longer have this symptom

I have never had this symptom

Sleep problems

Please tick the box that best describes this symptom after the operation when compared to how it was before the operation.

better worse no different

much better much worse

I no longer have this symptom

I have never had this symptom

Other symptoms that I had before the operation

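### The study-specific forms grade no symptom at baseline and record only recalled, surgery-anchored change afterwards, so headache, vision, hearing, balance and speech have no graded change and no like-for-like comparison with conservative patients

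*Supplement*

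**What the plan says.** Three secondary outcomes in section 4.4.2 of the protocol (version 1.2) concern symptom level or change:

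- Item 2: "Change of individual symptoms before and at 3, 12, 24 and 36 months following resection of SPC".
- Item 4: "Difference in severity of symptoms and QoL at baseline between patients who chose surgical and non-surgical treatment".
- Item 5: "Assessment of symptoms and QoL over (at diagnosis and 3, 12, 24 and 36 months later) in patients who chose not to undergo surgery".

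Section 3.2.2 says that symptom work in surgical patients will set assessments before surgery against those after it. Section 3.2.3 covers the "patient who chose conservative management at enrolment and at 3, 12, 24 and 36 months following the diagnosis of SPC" and adds a confounder-adjusted exploration of outcome differences between the cohorts. Section 3.3.2 wants a model that predicts improvement in symptoms as well as in QoL. Section 4.5.2 has both cohorts fill in symptom and QoL questionnaires at entry and at follow-up.

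The appended study-specific forms are the instruments. The pre-operative form uses yes/no, tick-box and free-text items, for example "Any memory problems? yes no". The 3- and 12-month forms are titled as post-operation forms. For each named symptom they instruct: "Please tick the box that best describes this symptom after the operation when compared to how it was before the operation".

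Separately, section 4.1 requires "Symptom category B (total score ≥5) according to" a published eight-item score that runs from 0 to 10. The protocol does not say that this score is repeated.

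**The concern.** A change from baseline needs the same quantity recorded at both times. The pre-operative form describes a symptom without saying how bad it is. The post-operative forms do not ask how bad the symptom is now. They ask the patient to compare now with a remembered state 3 or 12 months back. That judgement is made by unblinded patients who chose the operation, so it is open to recall and expectation bias.

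The items also refer to an operation, so a patient who had none cannot answer them. The symptom part of the between-cohort comparison then has no common measure on these forms.

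This matters because section 2 presents the study as better evidence than the published retrospective series and as a pilot for a randomised trial of surgery against conservative management. Table 1 summarises those series by the percentage of patients improved relative to before surgery. A recalled better/worse rating yields the same kind of figure. A randomised trial would need a symptom measure that works in both arms.

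**Working it through.** **The plan's own figure.** No sample size or precision is stated for symptoms. The only figure is for the primary outcome (section 4.4.1), and it reproduces:

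- SD of the difference = sqrt(42² + 18² − 2 × 0.5 × 42 × 18) = sqrt(1764 + 324 − 756) = sqrt(1332) = 36.50, stated as 36.
- For a 20-point change, two-sided 5% paired t-test and 90% power, the exact noncentral-t calculation gives n = 37 with either SD.

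That calculation concerns QLQ-C30 role functioning and does not bear on this point.

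**Item check.** The table sets the eight symptoms named on the 3- and 12-month forms against the other two instruments.

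| Symptom | Pre-operative form | 3- and 12-month forms | Specific graded QLQ-C30 item |
|---|---|---|---|
| Headache | type, site, triggers, timing | recalled change | none (general pain, items 9 and 19) |
| Vision | tick list, aggravating factors | recalled change | none |
| Hearing | side, noises, voices | recalled change | none |
| Dizziness/balance | type, time course, triggers | recalled change | none |
| Speech | yes/no, free text | recalled change | none |
| Memory | yes/no, free text | recalled change | item 25 |
| Concentration | yes/no, free text | recalled change | item 20 |
| Sleep | too much / too little / other | recalled change | item 11 |

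Counts:

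- Graded for severity at baseline on the study-specific form: 0 of 8.
- Rated by recall against the pre-operative state: 8 of 8.
- Covered by a specific four-level QLQ-C30 item: 3 of 8.
- Left without any specific graded measure at both times: 8 − 3 = 5.

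The only numeric score on the study-specific forms (1-10) is for new problems after the operation, so it has no baseline counterpart.

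**The entry score.** It has eight items with maximum 2+1+1+1+1+1+2+1 = 10. Since 5 or more is required, every participant's baseline total lies between 5 and 10. It gives some graded baseline severity, over a restricted range. With no stated repeat, it gives no change. Two of its items, loss of consciousness and transient neurological deficits, have neither a dedicated item on the post-operative forms nor a QLQ-C30 item.

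**Who could still benefit.** Under Amendment 1, 21 of the 40 surgical patients were operated on before the study began. A new baseline form can therefore reach at most 40 − 21 = 19 surgical patients (19/40 = 47.5%), and fewer if some have already had surgery when it is introduced. It can also reach conservative patients still to be enrolled.

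**The case against.** The strongest reply is that symptoms are in fact measured, and much of it stands.

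- The QLQ-C30 has four-level items on pain, rest, sleep, weakness, nausea, vomiting, tiredness, concentration and memory. They ask about the past week and can be given identically to both cohorts at every visit. It would be wrong to infer that symptom change cannot be measured at all, or that conservative patients have no usable symptom follow-up.
- The post-operative forms give an ordinal rating from much better to much worse, with options for a symptom that has gone or was never present. For symptoms whose presence was noted beforehand, that allows a crude before/after statement of resolution. It is a measure, though a recalled one. The forms also have space for three further symptoms named by the patient.
- The appendices are visible only in part. The forms shown are numbered 4 to 7, section 4.5.2 refers to Appendices 1-4, and the text ends with the 12-month form. Forms for the conservative cohort or for later visits may exist. One can say only that none is shown.
- Secondary outcome 6 predicts QoL improvement, which comes from the QLQ-C30. A reader might infer that the predictor model rests on recalled symptom change. Only the symptom-improvement part of 3.3.2 does.

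None of this gives headache, vision, hearing, balance or speech a graded value at two times, or a common measure across cohorts. The analysis plan that section 4.4.4 promises cannot supply it either, because an analysis plan cannot create data that were not collected.

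**Conclusion.** The point holds in a limited form. On the forms shown, five of the eight named symptoms have no graded change from baseline and no like-for-like comparison with conservative patients. Headache is among them, and it is one of only two entry-score items worth 2 points.

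The affected parts are secondary outcomes 2 and 5, outcome 4 as far as severity on these forms is concerned, the symptom part of 3.2.3, and the symptom-improvement part of 3.3.2. The primary outcome and its sample size are untouched. This is a worthwhile, inexpensive improvement and not a fatal flaw.

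The conclusion assumes that no unseen form grades these symptoms at baseline and follow-up, and that the entry score is not repeated. If either assumption is wrong, the gap narrows accordingly.

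A reader might also infer that repeating the entry score and making its change the main symptom outcome would be enough. The documents do not support that. Six of its eight items are scored 0 or 1, fatigue scores 0 for anything up to moderate, and hearing, speech and sleep are absent. Selection at 5 or more would also produce apparent improvement through regression to the mean.

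**What to change.** In section 4.5.2 and the appendices, add one short current-state symptom form, graded for example none / mild / moderate / severe over the past week. Word it without reference to an operation and give it identically at baseline and at each scheduled follow-up in both cohorts. It should cover the eight symptoms already on the post-operative forms plus the entry-score items not among them: nausea/vomiting, loss of consciousness, fatigue and transient deficits. Counting cognitive impairment as covered by memory and concentration, that is 8 + 4 = 12 items.

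In section 4.4.2, define the symptom outcome as within-patient change for each symptom. Keep the better/worse ratings as supportive. If the entry score is also repeated, report its change as supportive and note regression to the mean from the cut-off of 5.

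The same amendment should reconcile the visit schedule. Section 4.5.2 has questionnaires for conservative patients "at 3, 12, 26 and 36 months after the diagnosis" and uses the same months after surgery for surgical patients, while sections 3.2 and 4.4.2 have 24 months where 4.5.2 has 26.

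The cost is about 12 tick-box items per visit and a minor amendment. Patients operated on before the study have no such baseline, so their symptom change stays recall-based and should be reported separately.
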